4.2. Exclusion criteria

- Unable to provide informed consent
- Requires LTOT, defined by need for resting oxygen in the opinion of the local investigator
- Life expectancy <6 months
- On the active transplant list
- Previous acidotic hypercapnic respiratory failure (AHRF) requiring non-invasive ventilation (NIV)

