1.2.3. Justification for choice of intervention(s)

AOT is defined as oxygen used during physical activity, delivered by cylinders or concentrator, via either face mask or nasal cannulae, at a flow maintaining saturations $>90\%$ on oxygen, during the 6MWT. Current British Thoracic Society (BTS) oxygen guidance suggests that patients who desaturate on walking to $<88\%$ and are able to walk more or experience less dyspnoea with oxygen may benefit from AOT (37). Whilst the evidence on which this guidance was made is low grade and states that it should not be given routinely outside the context of LTOT, the end result has been extrapolation to any patient who desaturates, in part because the accompanying quality standards state that it may be ordered to improve mobility 'after appropriate formal assessment that includes an exercise test' (38). This standard does not specifically say that exercise duration or symptoms must decrease, so it is probable that expansion of AOT provision has occurred in any patient who has had exercise testing, in order to comply with this interpretation of the quality standard. Our trial team and collaborators agreed with this from their clinical practice. Consequently we have defined receipt of AOT as normal NHS care for those patients in the OXYPuF trial population who desaturate on exertion.

The comparator is standardised advice for breathlessness which is the provision of advice on use of appropriate pharmacological agents (e.g. morphine, benzodiazepines) and non-pharmacological interventions (e.g. fan, breathing techniques). A true placebo of medical air would be both expensive, logically difficult to blind (due to legal requirements for colouring of oxygen and air cylinders), and inappropriate in a pragmatic trial design, in which placebo effects on symptoms and activity that are separate from the biological effect of oxygen (i.e. correction of hypoxia) should occur in the group receiving AOT, and would occur in a real life context outside the trial. The advice about relief of breathlessness will be standardised and designed in conjunction with patients, and issued to both groups.

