3.2. Trial setting

The study is set in secondary care, enrolling participants from approximately 20 hospital outpatient clinics or community oxygen services with the trial intervention used by patients in their own homes. For the treatment arm, oxygen cylinders will be delivered to the participant's home for use in their day-to-day life, hence whilst initial assessment is in secondary care, treatment is received in the community.

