If the participant agrees to take part, the accelerometer will be sent via post (from the trials office) to the participant's home with instructions on how to use the accelerometer. They will be advised to wear the accelerometer at all times (except when in water) for 7 days. It is important to note that participating patients should be told that the accelerometer must be worn for 7 days post randomisation **prior to using the allocated trial intervention** and to then return it to the trials office by recorded delivery post after the 7-day period is completed.

Towards the end of the 6 month trial follow up period, prior to the 7 day period before the final study visit, an accelerometer will be sent via post to the participant. The accelerometer can be either returned via post to the trials office or handed to the research team at their final study visit (6 month follow up). The research team at site can then return the accelerometer via post to the trials office.

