4. ELIGIBILITY

4.1. Inclusion criteria

- Aged 18 or over
- Clinically diagnosed IPF, confirmed by an ILD multi-disciplinary team (MDT) linked to an NHS specialist commissioned IPF service
- Breathlessness with MRC dyspnoea score ≥2
- Willing and able to comply with completion of questionnaires out to 6 months post-randomisation
- Able to complete a 6MWT or 1 minute sit to stand test
- Able to use oxygen safely in the opinion of the local investigator

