6.1. Identification

Potential participants will be identified in respiratory and medical departments in participating NHS trust sites during regular scheduled outpatient visits. MDT lists will also be used to identify potential participants as well community based oxygen services. The charity 'Action Pulmonary Fibrosis' have also agreed to send an introductory letter to any charity members who may be interested in taking part in research. This letter will provide information about the trial and include an invitation to contact the appropriate research department for further information if they are interested in participating.

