7.9. Adherence

Adherence will be monitored via collecting the number and type of oxygen cylinders a patient is using per week. This information will be self-reported by the patient and included on the baseline and follow up forms.

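### The protocol reads as if participants are not on ambulatory oxygen at entry, but no eligibility criterion secures this, so current users can be randomised into a different comparison

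*Protocol*

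**What the plan says.** **Eligibility.** Protocol Section 4.2 has one exclusion about oxygen: "Requires LTOT, defined by need for resting oxygen in the opinion of the local investigator". The oxygen-related inclusion criterion in Section 4.1 is "Able to use oxygen safely in the opinion of the local investigator". Neither list, nor its copy in the trial summary, refers to current or past AOT. Screening in Section 6.2 covers medical history and contraindicated medications, the latter without definition. Section 1.2.1 says that expectations about earlier treatment were left out on purpose, to keep the population broad.

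**Recruitment.** Section 3.2 describes "enrolling participants from approximately 20 hospital outpatient clinics or community oxygen services", and Section 6.1 adds "MDT lists will also be used to identify potential participants as well community based oxygen services". Section 1.2.3 states: "Consequently we have defined receipt of AOT as normal NHS care for those patients in the OXYPuF trial population who desaturate on exertion".

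**Text that presupposes no AOT at entry.**
- Section 9: the AOT arm gets its oxygen prescription at the baseline visit, after randomisation, and receipt may take a further 2 to 3 weeks.
- Section 3.3.2: "the accelerometer must be worn for 7 days post randomisation", and the sentence goes on to require that this week comes before the allocated intervention is used. Section 8.2.2.3 repeats this.
- Section 7.6: control participants could be given AOT once the trial has ended.

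**Design and analysis.** The minimisation factors (Section 6.4) are centre, exertional desaturation, pulmonary rehabilitation and antifibrotic use. Section 15.2 adjusts for these and baseline K-BILD. The subgroups in Section 15.2.3 come from the same list plus the baseline exercise measures. AOT at entry appears in none of them.

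**The concern.** Section 2.2.1 asks whether K-BILD at 6 months is better after AOT than after advice alone. That needs a control arm without AOT and an intervention arm that starts it. A patient who already has cylinders at home meets every written criterion. If allocated to AOT, nothing changes for that patient, and both the baseline K-BILD and the baseline accelerometer week are already on treatment. If allocated to advice alone, the patient either keeps the oxygen, so that both arms are treated, or loses it, so that the contrast is the effect of stopping.

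The first case pulls the estimated difference towards zero. The second may push it up, because the trial is open-label, the outcome is patient-reported, and losing an existing treatment can lower control scores. Since the protocol does not say which applies, sites could differ, and the primary estimate could mix the two. A statistical analysis plan can add sensitivity analyses, but it cannot change who was randomised or what contrast they experienced.

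**Working it through.** **1. Reproduce the planned size.** Inputs from Section 15.1: difference 4.0, SD 8.85, 90% power, two-sided 5%, 20% dropout. Allocation is 1:1 (Section 6.3).

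n per arm = 2 × (1.960 + 1.282)² × 8.85² / 4.0² ≈ 102.9, so 103 by the normal approximation. The t-test version gives 103.84, so 104. Then 2 × 104 = 208, and 208 / 0.8 = 260. The stated figures reproduce, so the arithmetic is not in question. The target of 4.0 does, however, presume that every participant contributes an AOT versus no-AOT contrast.

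**2. Set the passages side by side.**

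| Question | Eligibility and recruitment text | Procedural text |
|---|---|---|
| Is a current AOT user eligible? | Not excluded (4.1, 4.2); oxygen services are a source (3.2, 6.1) | Prescription issued after randomisation (9) |
| Is the baseline off treatment? | Not required | Accelerometer week precedes the allocated intervention (3.3.2, 8.2.2.3) |
| Do controls have AOT during follow-up? | Existing supply not addressed | AOT for controls mentioned only for after the trial (7.6) |

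A current user allocated to AOT cannot meet the accelerometer requirement as it is meant, since that week would already be on oxygen. The right-hand column therefore holds only if entrants are not on AOT, and nothing in the middle column makes that so.

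**3. Illustrate dilution.** Let q be the share of participants already on AOT. The protocol gives no value, so q is assumed. Suppose these patients keep oxygen in both arms and contribute zero difference, and hold the SD at 8.85.

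Average difference = 4.0 × (1 − q). Standard error with 104 analysed per arm = 8.85 × √(2/104) = 1.227. Power = Φ(difference / 1.227 − 1.960). The last column inflates the normal-approximation size for 20% dropout.

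| q | Difference | Power | Recruited N for 90% power |
|---|---|---|---|
| 0 | 4.0 | 90.3% | 258 |
| 5% | 3.8 | 87.2% | 285 |
| 10% | 3.6 | 83.5% | 320 |
| 20% | 3.2 | 74.1% | 403 |
| 30% | 2.8 | 62.6% | 525 |

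Example at q = 20%: 3.2 / 1.227 − 1.960 = 0.647, and Φ(0.647) = 0.741. The 258 in the first row differs from the planned 260 only because it uses 103 rather than 104 per arm.

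**4. Withdrawal.** If controls lose existing oxygen, the effect on their K-BILD is the effect of stopping. The document gives no figure for it, so no calculation is possible.

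**The case against.** A reader might infer that the trial does enrol current AOT users and so does not test AOT against no AOT. The protocol does not support that. Their eligibility follows from silence in the criteria, not from any statement. Oxygen services also assess new referrals: Section 7.7.1 describes home oxygen assessment and review services, and Section 9 speaks of referral to the oxygen team after randomisation. The accelerometer and post-trial provisions show that an AOT-free entry was intended. This argument stands, and it limits the point to an assumption that is not written into eligibility.

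The protocol also defends its breadth: Section 1.2.1 wants results that apply to the whole UK IPF population. That justifies varied severity and co-treatment. It does not settle what the comparator is for someone already on the study treatment.

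A reader might also infer that current users could never be identified. That goes too far. Section 7.9 collects weekly cylinder use and says: "This information will be self-reported by the patient and included on the baseline and follow up forms". A baseline entry could identify them afterwards. However, the field is there for adherence, and the protocol plans no use of it for eligibility, balance or analysis. Desaturation and centre, both minimised, partly track prior AOT, and randomisation balances it in expectation. The issue is therefore which contrast is estimated, not confounding.

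Finally, the power figures rest on an assumed share and on users keeping oxygen in both arms, which fits Section 7.6 less well than withdrawal does. They are illustrations, not forecasts.

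**Conclusion.** The point holds as a gap between the eligibility criteria and the rest of the protocol, and it should be fixed; confidence is moderate. Followed literally, the criteria admit a current AOT user, and the protocol leaves that patient's supply in the advice-only arm undefined. Each such patient would contribute either no contrast or a withdrawal contrast, and neither answers the question in Section 2.2.1.

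The size depends on a share that the document does not give. At assumed shares of 10% to 30%, with zero contrast among users, SD 8.85 and 104 per arm, power would be about 84% to 63% instead of 90%. The withdrawal bias would probably run upwards but cannot be sized. If few or no current users present, the effect is negligible. The document therefore does not show that the primary comparison will fail, only that nothing in the written criteria prevents the problem.

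**What to change.** Reconcile Sections 3.2, 4.2 and 6.1 with Sections 3.3.2, 7.6, 8.2.2.3 and 9. The simplest route is to add to Section 4.2 and the trial summary an exclusion for patients currently prescribed or using AOT, with a matching check at screening in Section 6.2. This takes one eligibility line and one screening-log item by amendment. The price is a somewhat smaller recruitment pool, mainly at oxygen services.

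If the sponsor intends to include current users, the protocol should say so and state how their existing supply is treated in each arm; which arrangement applies is for the sponsor and clinicians to decide. Current AOT should then be recorded before randomisation and added as a minimisation factor and model covariate. That costs one randomisation field and small edits to Sections 6.4 and 15.2. It would balance and identify these patients, but would not turn their contrast into AOT versus no AOT, so the exclusion is the cleaner option.

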4.3. Co-enrolment

Enrolment to observational studies is permitted. In the case of interventional studies, where mutual agreement can be made between Chief Investigators that co-enrolment will not be harmful to the scientific integrity of either study this will also be allowed. We consider this an unlikely scenario, however what is more likely is that participating sites will use similar mechanisms to pre-screen or approach patients for multiple studies at once.

5. CONSENT

It is the responsibility of the Principal Investigator (PI) to obtain written informed consent for each participant prior to performing any trial related procedures. This task can be delegated by the PI to other members of the local research team, if local practice allows and this responsibility has been documented in the site signature and delegation log.

A Participant Information Sheet (PIS) will be provided to facilitate this process. The PI or delegate will ensure that they adequately explain the aim of the trial, the trial intervention, and the anticipated benefits and potential hazards of taking part in the trial to the participant. They will also explain that participation is voluntary and that the participant is free to decide to take part and may withdraw from the trial at any time. The participant will be given sufficient time to read the PIS and to discuss their participation with others outside of the site research team. The time period considered to be sufficient will be deemed locally at site by the research team. The participant will be given the opportunity to ask questions before signing and dating the latest version of the Informed Consent Form (ICF). If the participant then expresses an interest in participating in the trial, they will be asked to sign and date the

latest version of the ICF. The PI or delegate will then sign and date the ICF. A copy of the ICF will be given to the participant, a copy will be filed in the medical notes and the original placed in the Investigator Site File (ISF). Once the participant is entered into the trial, the participant's trial number will be entered on the ICF maintained in the ISF. In addition, the participant understands and acknowledges that, a copy of the signed ICF will be transferred to the trial team at BCTU for review.

Details of the informed consent discussions will be recorded in the participant's medical notes. This will include date of discussion, the name of the trial, summary of discussion, version number of the PIS given to participant, version number of ICF signed and date consent received. Where consent is obtained on the same day that the trial related assessments are due to start, a note should be made in the medical notes as to what time the consent was obtained and what time the procedures started.

At each visit the participant's willingness to continue in the trial will be ascertained and documented in the medical notes. Throughout the trial, the participant will have the opportunity to ask questions about the trial. Any new information that may be relevant to the participant's continued participation will be provided. Where new information becomes available which may affect the participants' decision to continue, participants will be given time to consider and if happy to continue they will be re-consented. Re-consent will be documented in the medical notes. The participant's right to withdraw from the trial will remain.

Electronic copies of the PIS and ICF will be available from the Trial Office and will be printed or photocopied onto the headed paper of the local institution.

If at any point during the trial the PI or suitably qualified delegate deems that the participant has lost capacity to provide willingness to continue in the trial, then the participant should be withdrawn from the trial using the change of status CRF.

There is an additional statement on the ICF for the participant to acknowledge that they understand that the Trial Office might in the future, for other related research, collect participant data available in NHS routine clinical datasets, including primary care data (e.g., Clinical Practice Research Datalink, The Health Improvement Network, QResearch) and secondary care data (Hospital Episode Statistics) through NHS Digital and other central UK NHS bodies. The participant will acknowledge that they understand that the Trial Office might send their name, address, date of birth and NHS number to the relevant national registry, and then for the national registry to link this to their data and send the information back to the Trial Office. The acknowledgement by the participant will also allow access to other new central UK NHS databases that will appear in the future. This will allow us (subject to receipt of additional funding via another grant application) to assess longer-term impact and health service usage data without needing further contact with the trial participants.

6. SCREENING, RANDOMISATION and BLINDING

6.1. Identification

Potential participants will be identified in respiratory and medical departments in participating NHS trust sites during regular scheduled outpatient visits. MDT lists will also be used to identify potential participants as well community based oxygen services. The charity 'Action Pulmonary Fibrosis' have also agreed to send an introductory letter to any charity members who may be interested in taking part in research. This letter will provide information about the trial and include an invitation to contact the appropriate research department for further information if they are interested in participating.

6.2. Screening

The research team will screen the patient for eligibility and record information on the **OXYPuF Participant Screening Log** accordingly. The following assessments form part of the screening process in order to confirm the patient's eligibility for participation in the OXYPuF trial:

- Medical History
- Contraindicated medications

Eligibility must be confirmed by a suitably qualified medical practitioner who is on the **OXYPuF Trial Signature and Delegation Log**.

Details of all patients approached about the trial will be recorded on the **OXYPuF Participant Screening Log** which will be kept in the ISF and should be available to be sent to the Trials Office upon request.

6.3. Randomisation

After participant eligibility has been confirmed, informed consent has been received and the baseline **OXYPuF Patient Completed Booklet** has been completed, the participant can be randomised into the trial. **OXYPuF Randomisation Notepads** will be provided to investigators and may be used to collate the necessary information prior to randomisation. All questions and data items on the **OXYPuF Randomisation Notepad** must be answered before a Trial Number can be given. If data items are missing, randomisation will be suspended, and can be restarted once the information is available. Only when all eligibility criteria and baseline data items have been provided will a Trial Number and treatment group be allocated.

Participants will be randomised in a 1:1 ratio to either AOT and standardised breathlessness advice or standardised breathlessness advice alone.

Those patients who are randomised to the intervention will receive AOT and standardised breathlessness advice. One week following randomisation, this group of patients will also receive a telephone call from the trials office to check fidelity of the intervention.

Those patients who are randomised to standardised breathlessness advice will receive standardised breathlessness advice.

6.4. Randomisation process

Randomisation will be provided by a secure online randomisation system at the Birmingham Clinical Trials Unit (BCTU) (available at <<insert web address>>), thereby ensuring allocation concealment. Unique log-in usernames and passwords will be provided to those who wish to use the online system and who have been delegated the role of randomising participants into the study as detailed on the **OXYPuF Trial Signature and Delegation Log**. These unique log-in details must not be shared with other staff and in no circumstances should staff at sites access either the randomisation process or clinical investigation database using another person's login details. The online randomisation system will be available 24 hours a day, 7 days a week, apart from short periods of scheduled maintenance. In the event of the online system not being available a telephone toll-free randomisation service ([name]) is available Monday to Friday, 09:00 to 17:00 UK time, except for bank holidays and University of Birmingham closed days. The availability of telephone randomisation may be reduced due to unforeseen circumstances such as epidemic/pandemic and/or natural disasters.

Following randomisation, a confirmatory e-mail will be sent to the randomiser, local PI, local Research Nurse, and trial manager.

The local research team should add the participant to the **OXYPuF Participant Recruitment and Identification Log** which links participants with their Registration/Trial Number. PIs must maintain this document securely and it must

not be submitted to the Trial Office. The *OXYPuF* Participant Recruitment and Identification Log should be held in strict confidence. [Randomisation method](#)

Participants will be randomised at the level of the individual in a 1:1 ratio to either AOT and standardised breathlessness advice or standardised breathlessness advice alone.

A minimisation algorithm will be used within the online randomisation system to ensure balance in the treatment allocations over the following variables:

- Centre
- Desaturation to <88% on 6MWT or equivalent exercise test
- Current or recent (within 6 months) pulmonary rehabilitation
- Current antifibrotic use

randomised To avoid the possibility of the intervention allocation becoming predictable, a random element will be included in the algorithm. Full details of the randomisation specification will be stored in a confidential document at BCTU.

